2. INTRODUCTION: BACKGROUND AND SCIENTIFIC RATIONALE

2.1. Background Information

Botanix Pharmaceuticals' BTX 1503 containing the active pharmaceutical ingredient, cannabidiol (CBD; *2-[(1R,6R)-6-isopropenyl-3-methylcyclohex-2-en-1-yl]-5-pentylbenzene-1,3-diol*) in a topical liquid formulation, is being developed for the treatment of acne vulgaris. CBD is a member of a broader family of compounds known as cannabinoids, a class of compounds originally derived from the *cannabis sativa* plant.¹ CBD is chemically synthesized under Good Manufacture Practices (GMP) for use in this study.

Synthetic CBD is not psychoactive and clinical trials have demonstrated that CBD may successfully treat epilepsy, arthritis, pain, and even Fragile X Syndrome.² Interest in CBD-based therapeutics has increased significantly in recent years, as published data has highlighted the potential efficacy and safety benefits of this compound.³ There are now more than 100 human clinical trials that have been completed, are underway, or pending recruitment around the world that are studying CBD in a range of diseases.⁴

No known well-controlled, human clinical studies have ever been conducted using CBD to treat skin disease, and no CBD containing pharmaceuticals have been approved to treat skin disease. Researchers have found that CBD may play a beneficial role in regulating the cutaneous endocannabinoid system by decreasing unwanted skin cell growth, sebum production and skin inflammation associated with many human skin diseases.¹

2.2. Rationale

2.2.1. Mechanism of Action

This study is intended to establish preliminary safety and tolerability in subjects with acne vulgaris treated with BTX 1503. The rationale for the use of BTX 1503 in acne is provided herein.

Acne is the most common skin disease in the world and is characterized by partial obstruction of the pores and associated local skin lesions that can appear on the face, chest or back.^{5,6} Obstructed pores can become enlarged and inflamed as sebum and its breakdown products accumulate, resulting in visible lesions that can be unsightly and cause permanent scarring.^{5,6} Acne usually begins in puberty and affects many adolescents and young adults, but it can occur at any stage of life. Approximately 85 percent of people between the ages of 12 and 24 experience at least minor acne.⁷ Acne often causes significant physical and psychological problems such as permanent scarring, poor self-image, depression and anxiety.⁸

Acne lesions are believed to result from an interaction of four primary pathogenic factors:

- the excessive production of sebum or lipids by sebaceous glands in the skin;
- hyper-proliferation of keratinocytes that contribute to clogging of pores through which sebum is normally released to the skin surface;

- colonization of the area in and around the sebaceous gland by bacteria; and
- inflammation, often associated with colonization by bacteria and their breakdown of sebum into irritating breakdown products.¹

For many years, treatment of acne has been dominated by the same four prescription pharmaceutical product classes:

- Antimicrobials. Antimicrobials for acne treatment target bacterial colonization and inflammation and are widely used topically and, in more severe disease, orally.⁸ While antimicrobials have been shown to be effective, there is a growing interest in limiting the use of antibiotics in acne, because of concerns regarding bacterial resistance.^{9,10,6}
- Retinoids. Topical retinoids address some of the changes in skin cells that contribute to clogging of the pores and are among the most commonly used prescription acne medications. Their limitations include skin irritation, photosensitization, and relatively modest efficacy in comparison with systemic therapies.¹⁰
- Isotretinoin. Oral isotretinoin (marketed initially as Accutane or Roaccutane) operates to significantly reduce sebum production and is indicated for the treatment of severe recalcitrant nodular acne. Even in the case of very severe disease, the efficacy of oral isotretinoin can be significant, with large proportions of patients achieving partial or complete clearance, after one course of therapy.^{8,11} However, oral isotretinoin is associated with significant systemic toxicity, including liver damage and severe birth defects, which largely limit its use as second line treatment in patients with severe disease who enroll in a monitoring program intended to restrict distribution of the drug. Mood disorders, depression, suicidal ideation and suicides have been reported in patients taking oral isotretinoin, but a causal relationship has not been established.^{8,12,13,14,15}
- Hormonal therapies. Oral agents that reduce the activity of sex hormones (called androgens) are also highly effective, as these treatments also reduce sebum production.¹⁶ Hormonal therapies have well-known systemic side effects, such as mood disturbance, loss of muscle mass and reduced sexual desire, that are related to their effects on sex hormones (they are most often used in the form of contraceptives). As such, they are not widely used in men or in women not seeking contraception.¹⁷

No topical treatments are currently available which target all the above pathogenic factors.¹⁸ Acne treatment guidelines recommend that acne treatment be directed toward as many of the four primary pathogenic factors as possible.¹⁹ Accordingly, patients are often treated with combination regimens that incorporate multiple agents with complementary mechanisms of action targeting different pathogenic factors.²⁰ While systemic therapies (such as isotretinoin) may inhibit sebum production, their use is limited by significant systemic side effects. An unmet need remains for effective therapies that are not associated with antibiotic resistance or treatment-limiting side effects, particularly therapies with novel mechanisms of action.⁹

BTX 1503 is focused on modulating the body's endocannabinoid system of receptors which regulate skin function, growth and renewal.²¹ It is understood that CBD may play a significant role in normalizing unwanted skin growth, reducing excessive production of oils and reducing inflammation and infection, amongst other functions.¹ Botanix Pharmaceuticals is exploring whether endocannabinoid modulating drugs (such as synthetic CBD) can be exploited in the management of acne.

BTX 1503 is a formulation of active synthetic CBD and inactive excipients designed to deliver a consistent dose of CBD to directly treat patients with acne. It is considered that CBD may:

- normalize excessive lipid synthesis of human sebocytes
- decrease proliferation (but not the viability) of these human sebocytes;
- inhibit hyperproliferation of keratinocytes;
- exert anti-inflammatory actions; and
- have anti-bacterial effects.^{1,22}

2.2.2. Nonclinical and Clinical Data

Nonclinical information on the safety pharmacology, pharmacokinetics and metabolism, and toxicology profiles of CBD has been extensively reported in the scientific literature. The clinical safety of CBD has also been established and reviewed in the published scientific literature. Clinical investigations with CBD have been reported in both normal subjects and patients, including treatment of individuals with oral doses of up to 300 mg/day (5 mg/kg/day or 185 mg/m²/day, for an individual with an average body weight of 60 kg). Higher oral doses of up to 1,500 mg/day (25 mg/kg/day or 925 mg/m²/day) have been reported to be well tolerated. CBD formulated as a topical gel (Zynerba Pharmaceuticals) for treatment of epilepsy has also been shown to be safe and well-tolerated with only mild, transient application site AEs observed.

Botanix Pharmaceuticals has conducted a Phase 1a single and multiple-ascending dose study (BTX 2017.001) of BTX 1503 in normal healthy volunteers in Australia involving 20 subjects. This study demonstrated that daily topical treatment with up to 3.75 mg/kg/day (225 mg CBD/day or 0.398 mg/cm²/day¹) applied as 3 mL of BTX 1503 5% (w/w) BID for 14 days was safe and well-tolerated. Forty-two (42) AEs were reported in 18 of the 20 participants. All AEs were reported as mild except one moderate vasovagal reaction to cannula insertion for blood draws (unrelated). Facial dryness and itchiness were the most frequently reported related AEs. One subject reported application site stinging, and one subject reported stinging in the eyes after accidental transfer of BTX 1503 into the eyes.

In a subsequent Australian Phase 1b open-label study (BTX.2017.002) of BTX 1503 in subjects with moderate to severe acne involving 21 subjects, daily topical treatment with up to 3.75

¹ Area of application assumed to be 565 cm² (*i.e.*, on the face), which is reported by the European Union Scientific Committee on Consumer Safety (SCCS) to be half of the surface area for a female head (SCCS Notes of Guidance for the Testing of Cosmetic Substances and Their Safety Evaluation, 8th edition, 2012; Table 2). Available at: http://ec.europa.eu/health/scientific_committees/consumer_safety/docs/sccs_s_006.pdf.

mg/kg/day (225 mg CBD/day or 0.398 mg/cm²/day) applied as 3 mL of BTX 1503 5% (w/w) BID for 28 days was shown to be safe and well-tolerated. There was only 1 AE associated with the study drug treatment; application site pain (sore eyes). Slight to moderate erythema was reported most frequently in cutaneous tolerability assessments. However, most subjects that reported erythema pre or post-study drug application had erythema at Baseline and treatment with BTX 1503 did not exacerbate the erythema. Only 1 subject had increased erythema from Baseline and this was reported at Day 35, seven days after their final application of study drug. Slight scaling was reported in 2 subjects (9.5%), slight dryness was reported in 4 subjects (19.0%) and slight burning/stinging was reported in 5 subjects (23.4%). Only 1 positive cutaneous tolerability assessment (slight dryness) was reported at more than a single visit.

In support of this planned Phase 2 clinical study, dermal toxicology studies of 90 days in duration in minipigs with BTX 1503 have not revealed any clinically significant toxicities or laboratory abnormalities. Details on the results of these studies are provided in the Investigator's Brochure.

The published literature has suggested that CBD may be an inhibitor of human cytochrome P450 CYP1A1 at concentrations that are 9.7-fold of observed maximum plasma concentrations (C_{max}) in clinical studies with BTX 1503.

The testes was the only target organ for toxicity identified in published studies in rats and monkeys: effects on sperm maturation were observed in a 25-day inhalation study in male rats [no-observed-adverse-effect level (NOAEL) of less than 0.6 mg CBD/kg/day (< 3.6 mg/m²/day) and lower testis weights and inhibition of spermatogenesis were observed at a daily oral dose of 300 mg/kg CBD/kg/day (3,600 mg/m²/day) in male monkeys. However, there were no changes in testis weight nor microscopic findings in the testes following 28 days of oral dosing in male rats at doses up to 400 mg/kg/day with the CBD to be used in the BTX 1503 formulations. The Area Under the Concentration (AUC) exposures are over 1000-fold higher than reported in clinical studies involving BID dosing with BTX 1503. In addition, there were no changes in testis weight nor microscopic correlates in the testes following 90 days of dermal dosing in minipigs using BTX 1503 at doses up to 150 mg/kg/day (AUC exposures in males at least 24-fold higher than observed in clinical studies with BTX 1503).

2.3. Rationale for Study

This study is designed to investigate the efficacy, safety and tolerability of BTX 1503 in subjects with moderate to severe acne. In this study, BTX 1503 will be applied at 3 different dosage regimens and compared against a Vehicle control. The treatment period will be 12 weeks to coincide with the FDA's recommended minimum treatment duration to demonstrate efficacy.

2.4. Potential Risks and Benefits

2.4.1. Known Potential Risks

Based on studies conducted by Botanix Pharmaceuticals, the potential risks associated with BTX 1503 include:

- Ocular irritation
- Local application site AE's
- Cutaneous reactions which may include erythema, dryness, scaling, and burning/stinging.

Facial dryness and facial itchiness were reported as possible effects of study drug treatment in Botanix Pharmaceuticals' healthy volunteer study (BTX.2017.001). In the current study, subjects will be allowed to use their usual moisturizers. Subjects in this study will be given instructions on what to do if BTX 1503 liquid accidentally gets into the eyes.

In the BTX.2017.002 study, slight to moderate erythema was reported most frequently in cutaneous tolerability assessments. However, most subjects that reported erythema pre-or post-study drug application had erythema at Baseline and treatment with BTX 1503 did not exacerbate the erythema. Only 1 subject had increased erythema from Baseline and this was reported at Day 35, seven days after their final application of study drug. Slight scaling was reported in 2 subjects (9.5%), slight dryness was reported in 4 subjects (19.0%) and slight burning/stinging was reported in 5 subjects (23.4%). Only one positive cutaneous tolerability assessment (slight dryness) was reported at more than a single visit.

In the published scientific literature, the only target organ for toxicity that has been identified was the testes in rat and monkey studies. It is uncertain if the reduction in spermatogenesis noted in these animal studies has a clinical correlate. In addition, this finding was not observed in the 28-day oral rat study or in a 90-day dermal minipig study conducted with Botanix Pharmaceuticals' BTX 1503.

The other aspect of systemic exposure to CBD reported in the published scientific literature was the potential for competitive binding to CYP450 isozymes, indicating a potential for drug-drug interactions. Given the limited systemic exposure observed in Botanix Pharmaceuticals' healthy volunteer study, the potential for a drug-drug interaction is considered to be minimal.

2.4.2. Known Potential Benefits

Non-clinical data suggests BTX 1503 may target pathways relevant in pathogenesis of acne. Activity of BTX 1503 was observed in the BTX.2017.002 study in subject with moderate to severe acne. Statistically significant improvements from Baseline in inflammatory and non-inflammatory lesion counts were observed. Improvements were also observed in the IGA and in the PRO. Although improvements in acne were observed in this 28-day treatment study, the benefit of BTX 1503 in patients with 12 weeks of treatment is unknown.

3. OBJECTIVE

The objective of this study is to assess safety and efficacy of various doses of BTX 1503 liquid formulation in subjects with moderate to severe acne vulgaris of the face.

4. STUDY DESIGN AND ENDPOINTS

4.1. Description of the Study Design

This is multi-center, randomized, double-blind, vehicle-controlled, parallel group, dose-finding study. Approximately 360 subjects will be enrolled.

4.2. Study Endpoints

4.2.1. Primary Efficacy Endpoint

The primary endpoint for the study is the absolute change from Baseline in inflammatory lesion counts at Day 84.

4.2.2. Secondary Endpoints

The secondary endpoints for the study are:

- Absolute change from Baseline in non-inflammatory lesion counts at Day 84,
- The percent change from Baseline in the inflammatory lesion counts at Day 84,
- The percent change from Baseline in the non-inflammatory lesion counts at Day 84,
- The proportion of subjects with an IGA score of “clear” or “almost clear” at Day 84,
- The proportion of subjects with at least a 2-grade reduction from the Baseline IGA score at Day 84, and
- The proportion of subjects with an IGA score of “clear” or “almost clear” at Day 84 and at least a 2-grade reduction from the Baseline IGA score.

4.2.3. Exploratory Endpoints

The exploratory endpoints for the study are:

- The change from Baseline in the total lesion count at Day 84,
- The percent change from Baseline in the total lesion count at Day 84,
- The change from baseline in the IGA scores and Day 84,
- The absolute and percent change from Baseline in inflammatory, non-inflammatory and total lesion counts at Day 14, Day 28 and Day 56.
- The proportion of subjects with at least a 2-grade reduction from the Baseline IGA score at Day 14, Day 28 and Day 56,
- The proportion of subjects with an IGA score of “clear” or “almost clear” at Day 14, Day 28 and Day 56,

- The proportion of subjects with an IGA score of “clear” or “almost clear” at Day 14, Day 28 and Day 56 and at least a 2-grade reduction from the Baseline IGA score.
- The change from Baseline in the Acne-QoL at Day 84, and
- Subject’s assessment of the change in their acne from Baseline to Day 84 (PRO).

4.2.4. Safety Endpoints

Safety for this study will be assessed by:

- Collection of reported adverse events throughout the study,
- Safety labs conducted at Baseline and Day 84,
- Monitoring of concomitant medications throughout the study,
- All women of childbearing potential (WOCBP) will have a urine pregnancy test (UPT) performed at the Baseline, Day 28, Day 56, and Day 84 Visits.

4.2.5. Cutaneous Tolerability

Cutaneous tolerability will be assessed at Baseline and each subsequent visit using a 4-point tolerability scale (0-3). Erythema, scaling, and dryness will be assessed by the investigator at Baseline and at each visit. Subjects will also be asked to rate symptoms of itching and burning/stinging over the preceding 24 hours at Baseline and subsequent visits using a 4-point (0-3) scale (see [Table 1](#)).

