6.1.5. Dosing and Administration

Subjects will receive their initial application of study drug on Day 1 at the clinical sites administered by the clinical site staff. When the subject is ready for study drug application, a pump is selected from the assigned study kit. The clinical site staff will remove the cap and apply the first dose of the study drug to the subject's entire face. All subsequent applications will be completed by the subject. To ensure that the entire face is covered, the study drug should be applied in a consistent manner for each application.

Subjects will be instructed in how to apply study drug. After their first application in the clinic subjects will apply their study drug at home. Each application of study drug will occur at the approximately the same time in the morning with the second application (for BID dosing groups) approximately 8 to 12 hours later. Subjects will apply study drug at the clinical site during the Day 14, Day 28, Day 56 and Day 84 Visits (final dose). A diary will be maintained documenting

compliance with the self-administered applications. All study drug bottles (used and unused) will be returned to the clinical site on the Day 28, Day 56, and Day 84 Visits.

Study drug should not be applied to the eyes or mouth. Subjects are to thoroughly wash their hands after study drug application. The study drug must not be handled by a family member or caregiver for study drug application.

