7. STUDY PROCEDURES AND SCHEDULE

7.1. Study Specific Procedures/Evaluations

At the Screening Visit (Visit 1), all subjects/legal guardians will review and sign an informed consent/assent form attesting to their knowledge of the study requirements, risks, and benefits. The following study specific procedures will occur for all subjects at the Screening Visit:

- Demographics, height, weight, and a medical history, including alcohol and tobacco use, will be obtained,
- A review of systems will be conducted by the principal investigator or designee,
- All WOCBP will have a UPT conducted. The test must be negative for the subject to be enrolled,
- A urine drug screen will be conducted to ensure that the subject is not taking drugs of abuse,
- A count of inflammatory and non-inflammatory lesions on the face and an IGA will be collected,
- The subjects will be queried for concomitant medications that they are currently taking. Concomitant medications include all prescribed and over the counter (OTC) medications and any supplements, and
- Eligibility criteria will be reviewed to determine if subjects may proceed to study enrollment.

If subjects are eligible upon screening, they may be enrolled into the study on the same day.

At various visits throughout the study, the following will occur for all subjects to monitor the safety of the study drug treatment:

- Blood draws will be conducted for CBC and chemistry analysis,
- Collection of urine will occur for a urinalysis,
- Cutaneous tolerability assessments will be conducted by the principal investigator or an appropriately trained designee. Cutaneous tolerability will be graded using the following scale: 0, None; 1, Slight; 2, Moderate; 3, Severe. Evaluation for, and grading of, the following will be done at each evaluation:
 - Erythema (investigator assessed),
 - Scaling (investigator assessed),
 - Dryness (investigator assessed),
 - Pruritus in last 24 hours (subject reported), and
 - Burning/Stinging in last 24 hours (subject reported).

The definition for each level of grading for each tolerability assessment is provided in [Table 1](#).

Table 1. Cutaneous Tolerability Assessments Scale for Acne Vulgaris

| Tolerability Assessment | Severity | | | |

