7.3.3. Study Drug Application Period

At the Day 1 Visit, subjects will receive their first study drug application at the clinical site during the visit. Subjects will be trained in the correct application of the study drug. Application of study drug should occur at approximately the same time each day. For subjects receiving BID dosing, the evening application should take place approximately 8 to 12 hours after the morning application. A diary will be maintained documenting compliance with the self-administered applications. At the Baseline, Day 28, and Day 56 Visits, the subject will be provided an ample supply of study drug to complete dosing for the next 28 days. Study drug will be applied at the clinical site during the Day 14, Day 28, Day 56 and Day 84 Visits (final dose) to ensure compliance with application instructions. Subjects will be instructed to not apply their study drug prior to the study visit.

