7.3.8. Schedule of Events Table – Subjects with Acne Vulgaris

The Schedule of Events is provided in [Table 3](#).

Table 3: Time and Events Schedule

| Parameter | Screening Visit (-35 to Day 1) | Baseline Visit (Day 1)^a | Day 14 Visit (Day 14 ±3 days) | Day 28 Visit (Day 28 ±5 days) | Day 56 Visit (Day 56 ±5 days) | Day 84 Visit^c (Day 84 ±5 days) |
|---------------------------------------------------|-------------------------------------------|----------------------------------------------------------------------------------|------------------------------------------|------------------------------------------|------------------------------------------|------------------------------------------------------|
| | Visit 1 | Visit 2 | Visit 3 | Visit 4 | Visit 5 | Visit 6 |
| Written informed consent/assent | X | | | | | |
| Medical history/ review of systems | X | | | | | |
| Demographics with Height and Weight | X | | | | | |
| Tobacco and Alcohol History | X | | | | | |
| Urine pregnancy test (WOCBP only) | X | X | | X | X | X |
| Eligibility criteria review | X | X | | | | |
| Safety Laboratory (CBC, chemistry and urinalysis) | | X | | | | X |
| Urine drug screening | X | X | | | | |
| Investigator's Global Assessment | X | X | X | X | X | X |
| Inflammatory and non-inflammatory lesion count | X | X | X | X | X | X |
| Photography of Face (selected sites) | | X | | | | X |
| Administer Acne-QoL | | X | | | | X |
| Administer PRO | | | | | | X |
| Ensure compliance with study drug administration | | | X | X | X | X |
| Study drug administration by site personnel (am) | | X | | | | |
| Study drug administration by subject | | Day 1 pm to Day 84 ^d ; Day 14, 28, 56, and 84 doses applied in clinic | | | | |
| Concomitant medications | X | X | X | X | X | X |
| Adverse events | | X | X | X | X | X |
| Cutaneous tolerability assessments ^b | | X | X | X | X | X |
| Dispense study drug and diary | | X | | X | X | |
| Collect diary and study drug | | | | X | X | X |

^a Screening and Baseline Visit may occur on the same day.

^b Assess cutaneous tolerability prior to and approximately 15 min after initial dose on Day 1 and the subject applications on Day 14, Day 28, Day 56, and Day 84

^c If subject discontinues treatment early, Day 84 evaluations will be performed when possible.

^d Subjects randomized to BID dosing will apply study drug in the morning and evening, 8 to 12 hours apart.

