None	xx (xx.x%)	xx (xx.x%)	xx (xx.x%)	xx (xx.x%)	xx (xx.x%)	xx (xx.x%)	xx (xx.x%)
Day 1 – 15 Mins Post-Dose							
n	xx	xx	xx	xx	xx	xx	xx
Severe	xx (xx.x%)	xx (xx.x%)	xx (xx.x%)	xx (xx.x%)	xx (xx.x%)	xx (xx.x%)	xx (xx.x%)
Moderate	xx (xx.x%)	xx (xx.x%)	xx (xx.x%)	xx (xx.x%)	xx (xx.x%)	xx (xx.x%)	xx (xx.x%)
Mild	xx (xx.x%)	xx (xx.x%)	xx (xx.x%)	xx (xx.x%)	xx (xx.x%)	xx (xx.x%)	xx (xx.x%)
None	xx (xx.x%)	xx (xx.x%)	xx (xx.x%)	xx (xx.x%)	xx (xx.x%)	xx (xx.x%)	xx (xx.x%)
Day 14 – Pre-Dose							
n	xx	xx	xx	xx	xx	xx	xx
Severe	xx (xx.x%)	xx (xx.x%)	xx (xx.x%)	xx (xx.x%)	xx (xx.x%)	xx (xx.x%)	xx (xx.x%)
Moderate	xx (xx.x%)	xx (xx.x%)	xx (xx.x%)	xx (xx.x%)	xx (xx.x%)	xx (xx.x%)	xx (xx.x%)
Mild	xx (xx.x%)	xx (xx.x%)	xx (xx.x%)	xx (xx.x%)	xx (xx.x%)	xx (xx.x%)	xx (xx.x%)
None	xx (xx.x%)	xx (xx.x%)	xx (xx.x%)	xx (xx.x%)	xx (xx.x%)	xx (xx.x%)	xx (xx.x%)

[Repeat for Day 14 – 15 Mins Post-Dose, Day 56 – Pre-Dose, Day 56 – 15 Mins Post-Dose, Day 84 – Pre-Dose, and Day 84 – 15 Mins Post-Dose]

[Repeat for Pruritus, Erythema, Dryness, and Scaling]

Note: Percentages are based on the number of subjects in each treatment group in the Safety population with a non-missing assessment at the given visit.

SOURCE: USERNAME/SPONSOR/PROJECT/JOBNAME (DATE,TIME)

Table 14.3.0.2.2: Summary of Cutaneous Tolerability Assessments Worst Post-Baseline Grades
(Safety Population)
(Page x of y)

Worst Post-Baseline Grade	Vehicle QD (N=xx)	Vehicle BID (N=xx)	Vehicle Combined (N=xx)	BTX 1503 5% BID (N=xx)	BTX 1503 5% QD (N=xx)	BTX 1503 2.5% QD (N=xx)	BTX 1503 Combined (N=xx)
Burning/Stinging							
n	xx	xx	xx	xx	xx	xx	xx
Severe	xx (xx.x%)	xx (xx.x%)	xx (xx.x%)	xx (xx.x%)	xx (xx.x%)	xx (xx.x%)	xx (xx.x%)
Moderate	xx (xx.x%)	xx (xx.x%)	xx (xx.x%)	xx (xx.x%)	xx (xx.x%)	xx (xx.x%)	xx (xx.x%)
Mild	xx (xx.x%)	xx (xx.x%)	xx (xx.x%)	xx (xx.x%)	xx (xx.x%)	xx (xx.x%)	xx (xx.x%)
None	xx (xx.x%)	xx (xx.x%)	xx (xx.x%)	xx (xx.x%)	xx (xx.x%)	xx (xx.x%)	xx (xx.x%)
Pruritus							
n	xx	xx	xx	xx	xx	xx	xx
Severe	xx (xx.x%)	xx (xx.x%)	xx (xx.x%)	xx (xx.x%)	xx (xx.x%)	xx (xx.x%)	xx (xx.x%)
Moderate	xx (xx.x%)	xx (xx.x%)	xx (xx.x%)	xx (xx.x%)	xx (xx.x%)	xx (xx.x%)	xx (xx.x%)
Mild	xx (xx.x%)	xx (xx.x%)	xx (xx.x%)	xx (xx.x%)	xx (xx.x%)	xx (xx.x%)	xx (xx.x%)
None	xx (xx.x%)	xx (xx.x%)	xx (xx.x%)	xx (xx.x%)	xx (xx.x%)	xx (xx.x%)	xx (xx.x%)
Erythema							
n	xx	xx	xx	xx	xx	xx	xx
Severe	xx (xx.x%)	xx (xx.x%)	xx (xx.x%)	xx (xx.x%)	xx (xx.x%)	xx (xx.x%)	xx (xx.x%)

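### Itch and burning/stinging keep a 24-hour recall at the 15-minute post-dose rating, so almost all of the period rated precedes the application

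*Protocol*

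**What the plan says.** **Recall.** Protocol 4.2.5 states: "Subjects will also be asked to rate symptoms of itching and burning/stinging over the preceding 24 hours at Baseline and subsequent visits". Section 7.1 and Table 1 attach the same 24 hours to pruritus and to burning/stinging. Section 7.1 gives one list of five items and says "Evaluation for, and grading of, the following will be done at each evaluation". No recall period is attached to the investigator-rated items (erythema, scaling, dryness).

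**Timing.** Table 3, footnote b: "Assess cutaneous tolerability prior to and approximately 15 min after initial dose on Day 1". The same pair of ratings is made around the subject's own application on Days 14, 28, 56 and 84 (sections 7.3.4 to 7.3.6).

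**Dosing around visits.** Section 6.1.5: "Each application of study drug will occur at the approximately the same time in the morning". BID subjects apply again about 8 to 12 hours later. Section 7.3.3: "Subjects will be instructed to not apply their study drug prior to the study visit".

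**Analysis.** SAP 6.1.2 defines Baseline as the last assessment before the first application. SAP 6.10.4.1 summarizes tolerability at each visit, the worst post-Baseline grade, and any mild, moderate or severe post-Baseline result. Shell 14.3.0.2.1 has separate pre-dose and post-dose rows. Its note on rows to repeat runs "Day 14 – 15 Mins Post-Dose, Day 56 – Pre-Dose", with nothing between for Day 28.

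**The concern.** A rating taken 15 minutes after an application is normally meant to show what the application did. Here the subject is asked about the previous day. Itch from the night before belongs in the post-dose answer as much as a sting felt a minute ago, and the two cannot be told apart when the older symptom is as strong or stronger. The pruritus anchors add to this: moderate and severe refer to disturbed sleep and to activities, which a reaction lasting minutes can hardly meet.

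Tolerability is one of the trial's stated purposes. Protocol 9.5 calls the sample size adequate for evaluating safety and tolerability, and the design compares dosing frequencies. Itching was among the most frequent related events in the healthy-volunteer study, and slight burning/stinging was reported in 5 of 21 subjects in the 28-day acne study (Protocol 2.2.2). These two items are where a signal might be expected.

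A second issue concerns the pre-dose rating. The morning dose is withheld until the visit, so a fixed 24-hour window may hold a different number of applications in QD and BID subjects.

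**Working it through.** The plan gives no figure to reproduce. The check is interval arithmetic on the stated times.

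**1. Overlap of the two windows.** Inputs: recall 24 h; post-dose rating 0.25 h after application. Let g be the hours from the pre-dose rating to the application (not stated; assumed 0 to 1 h).

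Overlap = [24 − (0.25 + g)] / 24

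| g | Shared hours | Overlap |
|---|---|---|
| 0 | 23.75 | 98.96% |
| 15 min | 23.50 | 97.92% |
| 30 min | 23.25 | 96.88% |
| 60 min | 22.75 | 94.79% |

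Whatever g is, the part of the post-dose window that follows the application is 0.25/24 = 1.04%.

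**2. Day 1.** No study drug has been applied before the clinic application, so 23.75 of the 24 hours are untreated in every arm. By SAP 6.1.2 the rating is post-Baseline, and neither SAP 6.10.4.1 nor shells 14.3.0.2.2 and 14.3.0.2.3 exclude it or subtract the Baseline grade. A subject with mild itch the evening before and none after the application can, on the literal wording, be counted as having mild post-Baseline pruritus.

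**3. Applications inside the pre-dose window, Days 14 to 84.** Let d be the hours by which the visit falls after the usual morning application. Visit clock times are not in the documents, so d is an assumption, shown from −2 to 8.

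- Hours since the last QD application: 24 + d
- Hours since the BID evening application: from 24 − 12 + d to 24 − 8 + d, that is 12 + d to 16 + d

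| d (h) | QD: hours since last | In 24 h? | BID evening dose: hours since | In 24 h? |
|---|---|---|---|---|
| −2 | 22 | yes | 10–14 | yes |
| 0 | 24 | at the limit | 12–16 | yes |
| 0.5 | 24.5 | no | 12.5–16.5 | yes |
| 2 | 26 | no | 14–18 | yes |
| 4 | 28 | no | 16–20 | yes |
| 8 | 32 | no | 20–24 | yes |

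For any d above 0 and up to 8, the QD window is empty and the BID window holds one application. QD arms hold 90 + 90 + 45 = 225 of 360 planned subjects. That is the number who could be exposed to this, not an estimate of how many would be.

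**4. Rows in shell 14.3.0.2.1.** Ratings are collected at 5 visits × 2 = 10 time points. The shell and its note cover Baseline, Day 1 post-dose, and both ratings on Days 14, 56 and 84: 1 + 1 + 2 × 3 = 8. The missing two are Day 28 pre-dose and post-dose, although section 7.3.5 collects them and SAP 6.10.4.1 asks for each visit.

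**The case against.** The strongest reply is that the ratings are paired. The two windows differ almost only by the minutes around the application, so a rise from pre-dose to post-dose within a visit points to the application. This stands. A reader might infer that the post-dose rating is blind to application-site reactions, and the documents do not support that. A reader might also infer that a sting must exceed the worst symptom of the previous day, but Table 1 does not say whether the 24-hour grade is the worst or the typical level. Masking needs an existing symptom of equal or higher grade. In the 28-day acne study only one positive assessment, of dryness, recurred at more than one visit, so masking may be uncommon, though that study had 21 subjects.

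The anchor problem is confined to pruritus. The burning/stinging anchors can be rated at 15 minutes.

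A reader might also infer that QD windows are often empty and that BID will therefore look worse. Without visit times, *often* is unsupported. Shells 14.3.0.2.1 to 14.3.0.2.3 also show Vehicle QD and Vehicle BID in separate columns, so a frequency-matched comparison of active with vehicle shares the same windows. Tolerability is summarized without tests, and adverse events, including local reactions, are sought at every contact (section 8.3).

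What the reply does not answer is the Day 1 rating. The worst-grade and any-grade tables do not use the pairing, and nothing in them removes a symptom that began before treatment.

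**Conclusion.** The point holds in a limited form. For two of the five tolerability items, about 99% of the post-dose recall precedes the application being rated (95% if the pre-dose rating is an hour before it). What is lost is separation of old from new symptoms, not all sensitivity. The clearest consequence is on Day 1, where an almost wholly untreated window enters the post-Baseline summaries in every arm. This rests on reading the 24-hour wording literally at both ratings, which is the only wording the documents give.

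The QD/BID difference in the pre-dose window is conditional on visits falling later than the usual dosing time, and its frequency is unknown. It bears on descriptive QD-versus-BID comparisons and on the Vehicle Combined column, which mixes 45 QD and 45 BID subjects. It does not bear on comparisons with the frequency-matched vehicle.

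The Day 28 omission is a separate slip in a table shell, and it contradicts the SAP's own text.

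**What to change.** 1. In Protocol 4.2.5, 7.1, Table 1 and the eCRF, define the 15-minute rating of pruritus and burning/stinging as *since the application just made*. For that rating, replace the pruritus anchors that refer to sleep and daily activities.
2. Keep the 24-hour recall for the pre-dose rating, so that it stays comparable with Baseline. Tying it to the last home application would not be an improvement: recall would then run 24 + d hours for QD against 12 + d to 16 + d for BID, a gap of 8 to 12 hours that again follows dosing frequency.
3. Record the clock time of the last home application before each visit. The documents describe a diary of doses applied, and SAP Listing 16.2.5.1 shows an administration time by visit, but they describe no time for the last home dose. Read pre-dose QD-versus-BID and Vehicle Combined comparisons of these two items with that time in view.
4. Add Day 28 pre-dose and 15-minute post-dose to the repeat note of SAP Table 14.3.0.2.1.

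Cost: item wording, one recorded time per visit and one shell line, with no added visit or procedure. The downside is that pre-dose and post-dose pruritus grades become less directly comparable. The post-dose change-from-Baseline summaries in Protocol 9.4.2 would also set a short recall against a 24-hour one for both items, and should carry a footnote saying so.
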